4.2. Inclusion/Exclusion Criteria

4.2.1. Inclusion Criteria

1. Diagnosis of MPS IIIA confirmed by the following methods:
 - a. No detectable or significantly reduced SGSH enzyme activity by leukocyte assay, and
 - b. Genomic DNA analysis demonstrating homozygous or compound heterozygous mutations in the SGSH gene
2. Cognitive Development Quotient (DQ) lower than 60 (calculated by Bayley Scales of Infant and Toddler Development - Third Edition)
3. Must be ambulatory, though may receive assistance with ambulation
4. Age range of 2 years up to 18 years (excluded).

4.2.2. Exclusion Criteria

1. Inability to participate in the clinical evaluation as determined by Principal Investigator

2. Identification of two nonsense or null variants on genetic testing of the SGSH gene
3. At least one S298P mutation in the SGSH gene
4. Has evidence of an attenuated phenotype of MPS IIIA
5. Presence of a concomitant medical condition that precludes lumbar puncture or use of anesthetics
6. Active viral infection based on clinical observations
7. Concomitant illness or requirement for chronic drug treatment that in the opinion of the PI creates unnecessary risks for gene transfer, or precludes the child from participating in the protocol assessments and follow-up
8. Participants with total anti-AAV9 antibody titers $\geq 1:100$ as determined by ELISA binding immunoassay
9. Participants with a positive response for the ELISPOT for T-cell responses to AAV9
10. Serology consistent with exposure to HIV, or serology consistent with active hepatitis B or C infection
11. Bleeding disorder or any other medical condition or circumstance in which a lumbar puncture (for collection of CSF) is contraindicated according to local institutional policy
12. Visual or hearing impairment sufficient to preclude cooperation with neurodevelopmental testing
13. Any item (braces, etc.) which would exclude the participant from being able to undergo MRI according to local institutional policy
14. Any other situation that precludes the participant from undergoing procedures required in this study
15. Participants with cardiomyopathy or significant congenital heart abnormalities
16. The presence of significant non-MPS IIIA related CNS impairment or behavioral disturbances that would confound the scientific rigor or interpretation of results of the study
17. Abnormal laboratory values Grade 2 or higher as defined in CTCAE v4.03 for GGT, total bilirubin (except in subjects diagnosed with Gilbert's syndrome), creatinine, hemoglobin, WBC count, platelet count, PT and aPTT
18. Female participant who is pregnant or demonstrates a positive urine or β hCG result at screening assessment (if applicable).
19. Any vaccination with viral-attenuated vaccines less than 30 days prior to the scheduled date of treatment (and use of prednisolone)
20. Previous treatment by Haematopoietic Stem Cell transplantation
21. Previous participation in a gene/cell therapy or ERT clinical trial.
22. Participants who are anticipated to undergo a procedure involving anesthesia within 6 months post- drug administration

23. Dysphagia present at Grade 3 or higher, as defined in CTCAE v4.03

NOTE: Potential participants with abnormal laboratory values may be re-screened for specific laboratory tests within the screening period (the 45 days prior to dosing) before being designated a screen failure. Repeat values within the normal range will be acceptable for inclusion.

4.3. Dosing Plan

This is a single dose open-label clinical trial. All participants will receive 3×10^{13} vg/kg of ABO-102 delivered one time through a venous catheter inserted into a peripheral limb vein.

4.4. Prior and Concomitant Therapy

All medicinal products that are already being prescribed to participants as common routine care will be continued during the clinical trial, with the exception of the prohibited medications listed in Section 4.4.1.

Any concomitant medications administered or discontinued during the study should be recorded on the eCRF.

In the event of an emergency, any needed medications may be prescribed without prior approval, but the medical monitor must be notified of the use of any excluded medications immediately thereafter.

4.4.1. Prohibited Medications

Any immune modifying medication other than the prescribed oral prednisolone (other than use of inhaled corticosteroids to manage chronic respiratory conditions) is prohibited.

5. STUDY PROCEDURES

5.1. Schedule of Evaluations

This clinical trial protocol is based in large part on observations from MPS IIIA and MPS IIIB participants enrolled in the observational study previously described, and the ABT-001 clinical trial which is currently ongoing (NCT02716246, EudraCT number 2015-003904-21).

Additionally, according to local regulatory requirements, a plan for vector shedding in blood and other body fluids is included as part of an environmental risk assessment.

For a general overview of the procedure and visits, please see the [Schedule of Evaluations](#).

5.2. Clinical Trial Documentation

All the information regarding study IMP request, shipment, storage, management and destruction is described in the study specific Pharmacy Manual.

The procedures that describe the collection, processing, labelling, storage, and shipment for the study samples are described in the Laboratory Manual. The study samples have been scheduled to allow a maximum blood volume of 35 ml per study visit, providing flexibility to the sites to reduce volume as per site policy if needed. Additional adhoc analysis on blood samples collected at any particular visit may be performed at the discretion of the PI.

5.3. Screening and Enrollment

5.3.1. Screening Visits 1 and 2 (Day -45 through Day -1)

The screening evaluations will take place over two visits (preferentially two weeks apart) to allow time for ELISA and ELISPOT results to be available before the participant undergoes sedation/anesthesia and other invasive clinical assessments, as the former tests present a significant chance of being exclusionary and the latter assessments puts the children under additional risks and therefore should not be conducted unless the probabilities to be enrolled in the trial are high.

Each screening visit may take place over multiple consecutive days if deemed necessary by the Principal Investigator to accommodate all the clinical assessments that need to be performed.

The following evaluations will be conducted during Screening Visit 1:

- Informed consent process
- Demographics (including age, gender, race, and date of birth)
- Medical history (general and MPS related)
- A complete physical examination with a head circumference measurement
- Adverse events (upon ICF signature)
- Concomitant medications
- Vital signs (temperature, respiratory rate, heart rate, blood pressure)

- Height and weight
- The participant will be CCI walking a 25-meter distance
- CCI
- Echocardiogram
- ECG
- Lab work will include:
 - Complete blood cell count (CBC) and differential
 - Electrolytes
 - Serum/plasma total protein
 - Albumin
 - Prothrombin time (PT), partial thromboplastin time (PTT), international normalized ratio (INR)
 - Creatinine/Blood urea nitrogen (BUN)
 - Aspartate aminotransferase (AST), alanine transaminase (ALT), serum/plasma gamma-glutamyl transpeptidase (serum/plasma GGT)
 - Alkaline phosphatase
 - Amylase
 - Serum/plasma total bilirubin
 - Random glucose
 - Troponin
 - Plasma and leukocyte SGSH enzyme activity levels
 - Plasma heparan sulfate levels
 - CCI
 - Urine GAG and heparan sulfate levels
 - Urinalysis
 - Urine or Serum pregnancy test (if applicable)
- Samples for vector shedding (urine, saliva and feces)
- ELISpots for T-cell responses to AAV9 and SGSH
- ELISA for detection of total antibodies to AAV9 and antibodies to SGSH
- CCI
- Confirm diagnosis of MPS IIIA via gene sequencing (if not previously done)
- Cognitive function and adaptive functioning assessment using:

- Neurocognitive validity form (initial set up for first scales)
- Vineland Adaptive Behavior Scale II- Survey form, parental rating of adaptive functioning
- Bayley Scales of Infant and Toddler Development – Version III - Cognitive, Language and Motor. If children obtain a developmental age older than 36 months with the Bayley, the Kaufman Assessment Battery for Children, Second Edition, will be used also and will replace the Bayley Scales in the next visits
- Pediatric Quality of Life Inventory (PedsQL™) Core Generic Scales for parents
- Pediatric Quality of Life Inventory PedsQL™ Gastrointestinal Symptoms Scales for parents

The neurocognitive evaluations at this visit and along all other visits during the study will be CCI to allow for the possibility of future auditing by an external psychologist.

The Vineland Adaptive Behaviour scale will always be the first cognitive/adaptive functioning scale to be used in all visits, to obtain an estimate of the child's developmental level that will help for following evaluations.

The KABC-II subtests required for the Fluid-Crystalized Index (FCI) will be administered. After the FCI is completed, the subtests required for the Nonverbal Index will be administered if the child is able to continue with the testing session.

The rater/s and parent participating on the evaluation should be consistently the same during the trial for each participant as much as possible. These assessments may be performed locally with an external rater, if the family signed the consent annex and there is a qualified rater trained for the study procedures.

- Modified Children's Sleep Habits Questionnaire (CSHQ)
- Parent Symptom Score Questionnaire, to collect list of symptoms and associated ranking.

Vector shedding samples for urine, feces and saliva are collected at Screening Visit 1. In the event that urine, saliva and/or feces samples are unable to be obtained at Screening Visit 1, they will be obtained at Screening Visit 2.

The following evaluations will be conducted during Screening Visit 2:

- Weight
 - The weight obtained at Screening Visit 2 will be used to calculate the viral vector dose
- Adverse events
- Concomitant medications

- CCI [REDACTED]
- Cognitive function and adaptive functioning assessment using:
 - Neurocognitive validity form (final set up for following scales)
 - Mullen Scales of Early Learning, both non-verbal assessments of cognitive function. If children obtain a developmental age older than 60 months with the Mullen, the Kaufman Assessment Battery for Children, Second Edition, will be used also and will replace the Mullen Scales in the next visits
 - CCI [REDACTED]
 - Parenting Stress Index, 4th Edition (PSI-4) short form
- Plasma and leukocyte SGSH enzyme activity levels
- Plasma heparan sulfate levels
- CCI [REDACTED]
- Abdominal MRI to measure liver and spleen volumes
- 45-min EEG
- Lumbar puncture (LP) will be performed
 - CSF analysis
 - SGSH enzyme activity
 - heparan sulfate levels
 - CCI [REDACTED]
 - protein, glucose, cell count and differential
 - CCI [REDACTED]
 - CSF biobanking
- Labs will be obtained, including:
 - Alpha-fetoprotein
 - Hepatitis (B, C) and HIV
 - Plasma biobanking
- Samples for vector shedding (plasma)
- The MRI and LP, CCI [REDACTED] will be performed while the participant is under a single sedation/anesthesia event under the direction of a qualified anesthesiologist. The same apply to other visits throughout the protocol.
- Vector shedding samples for plasma will be taken at Screening Visit 2. In the event that urine, saliva and/or feces samples are unable to be obtained at Screening Visit 1, they will be obtained at Screening Visit 2.

Scale	Development Age				Assessment performed by
	6-24 months	24-42 months	42-68 months	Above 68 months	
Vineland Adaptive Behavior Scale II- Survey form	X	X	X	X	Rater
CCI	X	X	X	X	Caregiver
Mullen Scales of Early Learning	X	X	X*		Rater
Bayley Scales of Infant and Toddler Development – Version III- Cognitive, Language and Motor	X	X			Rater
Kaufman Assessment Battery for Children, Second Edition			X*	X	Rater
PedsQL™ Core Generic Scales	X	X	X	X	Caregiver
PedsQL™ Gastrointestinal Symptoms Scales	X	X	X	X	Caregiver
PSI-4	X	X	X	X	Caregiver
CSHQ	X	X	X	X	Caregiver
Parent Global Impression Score	X	X	X	X	Caregiver
Clinical Global Impression Improvement Scale	X	X	X	X	Principal Investigator
Parent Symptom Score Questionnaire	X	X	X	X	Caregiver
Total number of scales	11	11	11	10	

* At least one assessment done in parallel for both scales to ensure a correct transition.

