
Exploratory Outcomes
	
 • CCI [REDACTED] █ [REDACTED] • CCI [REDACTED] • CCI [REDACTED] █ [REDACTED] █ [REDACTED]

Study Duration
	
Participants will be tested at baseline and return for follow up visits on Days 7, 14, 30, 60, 90, 180, and at 12, 18, and 24 Months for active monitoring.

Sample Size
	
This is an open label study in up to 12 participants with middle and advanced phase of MPS IIIA. Participants will receive a single intravascular infusion at a dose of 3×10^{13} vg/kg.

Statistical Analysis
	
This is a Phase I/II trial with safety and efficacy (change in CSF heparan sulfate levels and liver volume after treatment) as the primary outcomes. Secondary outcomes include additional efficacy measures several of which are exploratory. These include changes in heparan sulfate and/or total GAGs in plasma/urine, changes in SGSH enzymatic activity in CSF/leukocytes/plasma, changes in liver and brain volumes, changes in cognitive and behavioural measures, and changes in quality of life, sleep or seizures. Data of post-gene transfer monitoring will be compared with baseline data and a set of natural history data using the appropriate statistical analysis.
 
A final Statistical Analysis Plan will be prepared before the database lock, including a stratification of participants based on Age Equivalent scores above or below 18 months. This SAP will include an interim analysis to be conducted when all participants have reached Month 12 follow-up.

Long-term follow-up
	
After the 24-month visit, participants will be requested to participate in a long term follow up study (LTFU-ABO-102, EudraCT number 2019- 002979-34) consisting of monitoring for a minimum of 3 years for a total period of five years posttreatment.

TABLE OF CONTENTS

PROTOCOL AMENDMENT SUMMARY OF CHANGES TABLES.....	2
1. PROTOCOL SYNOPSIS	5
TABLE OF CONTENTS.....	9
SCHEDULE OF EVALUATIONS	12
2. LIST OF ABBREVIATIONS.....	17
3. INTRODUCTION.....	20
3.1. Background.....	20
3.2. Nonclinical Studies.....	20
3.3. Clinical Program.....	21
4. STUDY DESIGN	23
4.1. Study Population.....	23
4.2. Inclusion/Exclusion Criteria	23
4.2.1. Inclusion Criteria	23
4.2.2. Exclusion Criteria	23
4.3. Dosing Plan.....	25
4.4. Prior and Concomitant Therapy.....	25
4.4.1. Prohibited Medications.....	25
5. STUDY PROCEDURES.....	26
5.1. Schedule of Evaluations	26
5.2. Clinical Trial Documentation	26

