PT/INR/PTT	X		X		X		X	X	X				X					X	X	X	X
Creatinine/BUN	X		X		X		X	X	X				X					X	X	X	X
AST/ALT	X		X		X		X	X	X	X	X	X	X	X	X	X	X	X	X	X	X
Serum/plasma GGT	X		X		X		X	X	X	X	X	X	X	X	X	X	X	X	X	X	X
Alkaline phosphatase	X		X		X		X	X	X				X					X	X	X	X
Alpha-fetoprotein		X											X					X	X	X	X
Amylase	X		X		X		X	X	X	X ¹⁰	X ¹⁰	X ¹⁰	X ¹⁰	X ¹⁰	X ¹⁰	X ¹⁰	X ¹⁰	X ¹⁰	X ¹⁰	X ¹⁰	X ¹⁰
Serum/plasma total bilirubin	X		X		X		X	X	X				X					X	X	X	X
Random glucose	X		X		X		X	X	X				X					X	X	X	X
Troponin	X		X		X		X	X	X		X		X					X	X	X	X
Plasma and leukocyte SGSH enzyme activity levels	X	X					X	X	X		X		X					X	X	X	X

STUDY TIMELINE OF EVENTS																					
Study Interval	Screening		Pre Infusion Visit	Hospital Admission/ Vector Injection (Inpatient)	Inpatient	Follow-Up (Outpatient)															
	Visit #	Visit 1				Visit 2	Visit 3		Visit 4	Visit 5	Visit 6	Labs	Visit 7	Labs	Visit 8	Labs	Labs	Labs	Visit 9	Visit 10	Visit 11
Study Procedures	Day -45 through -1		Day -1	Day 0	Day 1 (24 hrs)	Day 2 (48 hrs)	Day 7 +/- 2 days	Day 14 +/- 2 days	Day 30 +/- 3 days	Day 45 +/- 3 days	Day 60 +/- 7 days	Day 75 +/- 3 days	Day 90 +/- 7 days	2 weeks post steroids +/- 7 days	Day 120 +/- 7 days	Day 150 +/- 7 days	Day 180 +/- 21 days	Month 12 +/- 30 days	Month 18 +/- 30 days	Month 24 +/- 30 days	
Urine GAG/heparan sulfate levels	X				X		X	X	X			X						X	X	X	X
Raw plasma heparan sulfate	X	X			X		X	X	X			X						X	X	X	X
Urinalysis	X				X		X	X	X				X					X	X	X	X
Vector Shedding Samples: Plasma, Urine, Feces, Saliva	X ⁵	X ⁵		X ⁶	X	X	X	X	X		X ⁷		X ⁷					X ⁷	X ⁷	X ⁷	X ⁷
Urine or Serum pregnancy test (if applicable)	X			X															X		X
Gene sequencing to confirm MPS IIIA diagnosis	X ⁸																				
ELISpot	X							X	X	X ¹⁷	X	X ¹⁷	X	X ¹⁷	X ¹⁷			X	X	X	X
ELISA	X						X	X	X		X		X					X	X	X	X
Plasma biobanking		X		X			X	X	X		X		X					X	X	X	X
CCI	X				X		X	X	X		X							X	X	X	X
Serum nAbs	X																	X	X		X
Serology: hepatitis B, C, and HIV		X																			
Sedation/Anesthesia		X		X ³					X									X	X		X
Lumbar puncture		X							X									X	X		X
CSF enzyme activity & heparan sulfate levels		X							X									X	X		X
CSF protein, glucose, cell count and diff		X							X									X	X		X
CCI		X							X									X	X		X
CCI		X							X									X	X		X
CSF Biobanking		X							X									X	X		X
Brain MRI		X																	X		X

STUDY TIMELINE OF EVENTS

Study Interval	Screening		Pre Infusion Visit	Hospital Admission/ Vector Injection (Inpatient)	Inpatient	Follow-Up (Outpatient)														

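### HIV and hepatitis B/C serology is exclusionary but is first drawn at Screening Visit 2, the sedation, MRI and lumbar-puncture visit, and its result is not required before that sedation

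*Protocol*

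**What the plan says.** Protocol Section 4.2.2, criterion 10 (repeated in the Synopsis), excludes children with "Serology consistent with exposure to HIV, or serology consistent with active hepatitis B or C infection".

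Section 5.3.1 spreads screening over two visits between Day -45 and Day -1. The stated purpose is "to allow time for ELISA and ELISPOT results to be available before the participant undergoes sedation/anesthesia and other invasive clinical assessments". The reason given is that ELISA and ELISpot have a significant chance of excluding the child, while the invasive assessments add risk and "therefore should not be conducted unless the probabilities to be enrolled in the trial are high".

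The serology item, "Hepatitis (B, C) and HIV", is in the Screening Visit 2 lab list of Section 5.3.1 and absent from the Visit 1 list. The row "Serology: hepatitis B, C, and HIV" in the protocol's Schedule of Evaluations has one mark, under Visit 2. SAP Table 1 (Section 3.2) has the same.

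At Visit 2 the MRI and lumbar puncture "will be performed while the participant is under a single sedation/anesthesia event under the direction of a qualified anesthesiologist". Section 5.3.1 also says: "Each screening visit may take place over multiple consecutive days if deemed necessary by the Principal Investigator".

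**The concern.** A test that can exclude a child is most useful before the riskiest screening procedures. Here it is first drawn at the visit where those procedures take place, and no sentence puts the result ahead of them. A child who later proves ineligible under criterion 10 may therefore already have had an anesthetic, MRI and a lumbar puncture with no prospect of treatment in the trial. Section 8.2 expects that these children cannot consent or assent for themselves, which makes unnecessary procedures harder to justify. A screen failure of this kind would also use scan time and CSF assays.

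The stake is procedural risk at screening. The efficacy and safety analyses are not touched.

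**Working it through.** There is no planned figure to reproduce. The check is a comparison of passages, followed by an illustrative calculation.

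**Step 1. Where each laboratory eligibility test is first drawn** (Sections 4.2.1, 4.2.2 and 5.3.1)

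| Criterion | Test | First drawn |
|---|---|---|
| Inclusion 1a | Leukocyte SGSH activity | Visit 1 |
| Inclusion 1b | Gene sequencing, if not already documented | Visit 1 |
| Exclusion 8 | Anti-AAV9 antibodies by ELISA | Visit 1 |
| Exclusion 9 | ELISpot to AAV9 | Visit 1 |
| Exclusion 10 | HIV, hepatitis B and C serology | **Visit 2** |
| Exclusion 17 | GGT, bilirubin, creatinine, blood counts, coagulation | Visit 1 |
| Exclusion 18 | Pregnancy test, if applicable | Visit 1 |

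The other legible Visit 2 laboratory items are SGSH activity and plasma heparan sulfate (both also at Visit 1), alpha-fetoprotein, the CSF analyses, biobanking and the plasma shedding sample. None is a first draw for an eligibility criterion. Some Visit 2 entries are redacted, so this covers the legible text only.

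**Step 2. Is the serology result required before sedation?** The opening of Section 5.3.1 names ELISA and ELISpot. The Visit 2 list sets no order between the blood draw and the sedation. Section 5.3.2 requires all criteria to be passed before the prophylactic steroid starts on Day -1. That protects the dosing decision, but comes after the Visit 2 procedures. No other sentence fills the gap.

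**Step 3. How many children?** Inputs:
- n = 12, from the Synopsis: "This is an open label study in up to 12 participants with middle and advanced phase of MPS IIIA". This counts participants, not children who reach Visit 2. The documents give no screening count.
- p = proportion with exclusionary serology. The documents give none; 0.5% to 2% is assumed, with 0.1% as a lower sensitivity value.

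Expected number = n × p. Chance of at least one = 1 − (1 − p)^n.

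| n | p | Expected number | Chance of at least one |
|---|---|---|---|
| 12 | 0.1% | 12 × 0.001 = 0.012 | 1.2% |
| 12 | 0.5% | 12 × 0.005 = 0.06 | 5.8% |
| 12 | 2% | 12 × 0.02 = 0.24 | 21.5% |
| 20 | 0.5% | 20 × 0.005 = 0.10 | 9.5% |
| 20 | 2% | 20 × 0.02 = 0.40 | 33.2% |

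The rows with n = 20 show the effect of more children reaching Visit 2 than are enrolled; 20 is an assumption. These are upper figures for avoidable procedures, since a site that obtained the result first would avoid them.

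**The case against.** **The stated reason for two visits is narrower than serology.** Section 5.3.1 names ELISA and ELISpot because they often exclude, and asks only that enrollment be likely before invasive work. At the assumed prevalence, 98% to 99.5% of children pass criterion 10, so serology hardly moves the probability of enrollment. This stands. A reader might infer that the Visit 2 draw contradicts the protocol's own reason for two visits. The documents do not support that: there is no rule about serology to break, and the tension is only with the general principle. That principle still favors an early draw, and tests that section does not single out, such as creatinine and the pregnancy test, are already placed at Visit 1.

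**A site can get the result in time.** A visit may run over several days. Visit 2 includes work not listed under the sedation event, such as weight, the Mullen scales and an EEG that the outcome list describes as awake. Section 5.2 lets the investigator order additional analyses on blood from any visit, arguably including serology on Visit 1 blood. This also stands. A reader might infer that serology can never screen out a child before anesthesia; that is too strong. What remains is that the protection is optional and depends on the site.

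**Eligibility need only be settled before steroid and dosing.** This is true for treatment decisions, and the Visit 2 draw satisfies it. It does not address the risk of the screening procedures themselves.

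**The practical effect is now small.** SAP Section 5.1 reports that the study was terminated with 5 enrolled, all treated. This lowers the urgency but leaves the description of the schedule correct.

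**Conclusion.** The point holds as a minor design weakness. Among the legible laboratory eligibility tests, HIV and hepatitis B/C serology is the only one first drawn at the sedation, MRI and lumbar-puncture visit, and the protocol does not require its result before that sedation. An avoidable anesthetic, MRI and lumbar puncture are therefore possible, though not inevitable.

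The expected number of children with exclusionary serology is 0.06 to 0.24 among 12. This rests on an assumed prevalence of 0.5% to 2% and on 12 children reaching Visit 2. The documents do not show that any child was in fact affected, because they report no screening failures by reason. No endpoint, estimate or dosing-eligibility decision changes.

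**What to change.** In protocol Section 5.3.1, move hepatitis B/C and HIV serology from the Visit 2 labs to the Visit 1 labs, and add it to the results that must be available before the Visit 2 sedation. Move the mark in the Schedule of Evaluations to Visit 1 and align SAP Table 1. If the draw stays at Visit 2, the minimum is a sentence requiring the result before the sedation.

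Costs:
- **Blood volume.** Visit 1 gains a small draw and Visit 2 loses it. Section 5.2 caps blood at 35 mL per visit, and Visit 1 already has a long lab list. The documents give no volumes per test, so the fit must be checked against the Laboratory Manual; the saving at Visit 2 does not help with the cap at Visit 1.
- **Extra tests.** Serology would be run on some children who then fail ELISA or ELISpot.
- **Under the minimum option,** the sedation must wait for the result, whose turnaround time is not stated.

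Both visits lie in the same Day -45 to -1 window, so an earlier draw remains within screening. With the study terminated, the change mainly matters if this screening schedule is reused; the SAP edit is for consistency and alters no analysis.
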